7.1.5.3.2. Sponsor Responsibility

If a serious unexpected adverse event is believed to be related to the study drug or study procedures, the Sponsor will take appropriate steps to notify all investigators participating in sponsored clinical studies of TV-45070 and the appropriate regulatory authorities.

In addition to notifying the investigators and regulatory authorities, other measures may be required, including the following:

- altering existing research by modifying the protocol
- discontinuing or suspending the study
- altering the process of informed consent by modifying the existing consent form and informing current study participants of new findings
- modifying listings of expected toxicities to include adverse events newly identified as related to TV-45070

7.1.6. Protocol-Defined Adverse Events for Expedited Reporting

No protocol-defined adverse events for expedited reporting were identified for this study.

7.1.7. Withdrawal Due to an Adverse Event

Any patient who experiences an adverse event may be withdrawn from study drug treatment at any time at the discretion of the investigator. If a patient is withdrawn wholly or in part because of an adverse event, both the adverse events page and the termination page of the CRF will be completed at that time. If possible, a blood sample will be obtained for the measurement of study drug concentrations.

The patient will be monitored at the discretion of the investigator (eg, until the event has resolved or stabilized, until the patient is referred to the care of a health care professional, or until a determination of a cause unrelated to the study drug or study procedure is made). The investigator must inform the CPP/CL as soon as possible of all patients who are being considered for withdrawal due to adverse events. Additional reports must be provided when requested.

If a patient is withdrawn from study drug treatment and/or the study for multiple reasons that include adverse events, the termination page of the CRF should indicate that the withdrawal was related to an adverse event. An exception to this requirement will be the occurrence of an adverse event that, in the opinion of the investigator, is not severe enough to warrant

discontinuation but that requires the use of a prohibited medication, thereby requiring discontinuation of the patient. In such a case, the reason for discontinuation would be need to take a prohibited medication, not the adverse event.

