5.3. Prior and Concomitant Therapy or Medication

Any prior or concomitant therapy or medication that a patient has had within 90 days before study drug administration and up to the end of the study period, including follow-up, will be recorded on the CRF. Generic or trade name, indication, and dosage will be recorded. The Sponsor will encode all therapy and medication according to the World Health Organization drug dictionary (WHO Drug).

The following medications will not be allowed during this study:

- Oral analgesics
- Topical analgesics, including lidocaine (gels, creams and patches) and capsaicin patches
- Rescue pain medication except permitted acetaminophen rescue
- Class Ic anti-arrhythmic drugs such as flecainide or propafenone

At each clinic visit after the screening visit, the investigator will ask patients whether they have taken any medications (other than study drug), including OTC medications, vitamins, or herbal or nutritional supplements, since the previous visit. Indication, dosage, and start and end dates should be entered on the CRF.

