### 6.2.3. Sensitivity Analysis

Two sensitivity analyses will be performed in order to assess the robustness of the results of the primary analysis to changes in the assumptions and data characteristics. The first sensitivity analysis is a multiple imputation method to handle missing weekly average of the daily average NRS pain scores for week 4. Consistent with the recommendations of the National Academy of Sciences report (National Research Council 2010), under the assumption of missing at random (MAR) and taking into account of potential bias towards the active arm for patients who withdrew from the study due to adverse events, the following steps will be carried out in SAS using the MI, Mixed, and MIANALYZE procedures:

- Step 1: prepare data set for MI procedure (PROC MI)

The following auxiliary variables are to be included in the model for PROC MI:

- Treatment (1=placebo, 2=TV45070 4%, 3=TV45070 8%)
- R1150W genotype (1=AA, 2=GA, 3=GG)
- All observed pain scores, screening, baseline, and weekly averages at each post randomization week (week 1, week 2, week 3, week 4)

The treatment will be coded to 1 (placebo) for those in the active arms withdrawn from study due to an adverse event or lack of efficacy. Thus, the missing week 4 pain scores will be imputed based on the observed placebo patient's data. In order to adjust for the use of rescue medication at week 4, the average weekly pain intensity at week 4 will be set to missing for patients who used an excessive amount of rescue medication during the week before the multiple imputation. Excessive use of rescue medication is defined as the use of rescue medication on at least 4 out of 7 days of the week 4 treatment.

- Step 2: run PROC MI. The following SAS code may be used to generate the imputed data sets:

```

Proc mi data=datain nimpute=5 seed=598719001 out=mi_out
  Maximum=10 minimum=0 round=0.01;
  Class treat genotype;
  Var treat genotype screening baseline week1 week2 week3 week4;
  Monotone reg;

```

Run;

Note: if the missing data pattern is not monotonic, a Markov Chain Monte Carlo (MCMC) method will be used instead of a regression method for imputing missing data. R1150W genotype will be used, with all 3 possible categories.

- Step 3: run mixed procedure (PROC MIXED) using the data from PROC MI

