**Table 2: Imputation Methods for Weekly Average of the Daily Average NRS Pain Scores**

Double-blind Treatment	Reason	Efficacy Analysis	
		Sensitivity 1	Sensitivity 2
Placebo	Discontinued due to AE or Lack of Efficacy	Multiple imputation	Baseline (BOCF)
	Discontinued due to all other reasons	Multiple imputation	Multiple imputation
	Completed study but took excessive rescue medication before week 4 visit	Multiple imputation	Multiple imputation
TV-45070	Discontinued due to any AE or Lack of Efficacy	Multiple imputation with treatment code set to placebo	Baseline (BOCF)
	Discontinued due to other reasons	Multiple imputation	Multiple imputation
	Completed study but took excessive rescue medication before week 4 visit	Multiple imputation	Multiple imputation

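### Patients who stop because a milder adverse event needs a prohibited drug are coded as non-AE withdrawals, so both sensitivity analyses impute them under their own treatment code; the effect is probably small and cheap to close

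*Protocol*

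**What the plan says.** Protocol 7.1.7 sets a default and an exception for the withdrawal reason. By default, when an AE is one of several reasons, "the termination page of the CRF should indicate that the withdrawal was related to an adverse event". The exception is an AE that the investigator does not consider severe enough to justify "discontinuation but that requires the use of a prohibited medication, thereby requiring discontinuation of the patient". For that case the protocol states: "In such a case, the reason for discontinuation would be need to take a prohibited medication, not the adverse event".

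Protocol 5.3 introduces its list with "The following medications will not be allowed during this study" and names four categories. Three are pain treatments: oral analgesics, "Topical analgesics, including lidocaine (gels, creams and patches) and capsaicin patches", and "Rescue pain medication except permitted acetaminophen rescue". The fourth is Class Ic anti-arrhythmics.

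SAP 6.2.3 uses the discontinuation reason as the switch in both sensitivity analyses. In the first, the treatment code is set to placebo "for those in the active arms withdrawn from study due to an adverse event or lack of efficacy". In the second, the same two reasons lead to baseline observation carried forward (BOCF) in every arm. For the TV-45070 arms, Table 2 gives the row "Discontinued due to other reasons" ordinary multiple imputation in both analyses, and the placebo row for the remaining reasons does the same. The SAP has no row for prohibited-medication withdrawals and does not mention the 7.1.7 exception.

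**The concern.** SAP 6.2.3 says the first sensitivity analysis is meant to allow for bias in favour of the active arms when patients leave because of AEs. Patients under the 7.1.7 exception left because an AE led to a treatment they could not take on study, yet their recorded reason takes them out of the conservative row. They are imputed as missing at random under their own treatment code, as they are implicitly in the primary MMRM. No analysis of the primary endpoint visible in the documents treats them more cautiously.

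No later pain data can correct this. The eDiary is collected at the early termination visit, and Protocol 4.4 says efficacy data obtained after the specified time are not analysed. Since most of the prohibited categories are pain treatments, some of these exits may well be informative for a pain endpoint.

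The same coding could also keep such cases out of SAP Table 15.3.8, the summary of AEs causing discontinuation. This depends on which CRF field feeds that table, and the SAP does not say.

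**Working it through.** **The plan's own figure.** Inputs from Protocol 9.2: difference 1.0, SD 2.35, two-sided 0.05, power 80%, dropout 20%.

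- The normal approximation gives 87 per arm. With the t distribution, power is 0.797 at 87 and 0.802 at 88, so 88 is right.
- 88 / 0.80 = 110 randomized per arm. The plan's figures reproduce.
- Planned dropouts per arm: 0.20 × 110 = 22.
- Yardstick SE of a between-arm difference: 2.35 × √(2/110) = 0.317.

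**Routing.** The 7.1.7 exception gives a non-AE reason. A non-AE reason that is not lack of efficacy falls in Table 2's remaining-reasons row. That row gives own-code multiple imputation in both analyses. This follows from the text alone, provided the SAP takes its reasons from the CRF termination page.

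**Size.** The documents do not give the quantities below, so all are assumed and shown as ranges: f, the share of an arm routed this way; g, the gap between own-code and placebo-coded imputed week 4 means; p, mean placebo improvement. Each shift is how far the active-versus-placebo contrast would fall if these patients were handled like AE withdrawals.

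First sensitivity analysis: shift = f × g. Only the active arm matters, because recoding to placebo changes nothing for placebo patients.

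| f | patients of 110 | g = 1.0 | in SE | g = 0.2 |
|---|---|---|---|---|
| 2% | 2.2 | 0.020 | 0.06 | 0.004 |
| 5% | 5.5 | 0.050 | 0.16 | 0.010 |
| 10% | 11 | 0.100 | 0.32 | 0.020 |
| 20% (every planned dropout) | 22 | 0.200 | 0.63 | 0.040 |

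Here g = 1.0 is the full design effect. The value g = 0.2 stands for patients with several weeks observed, where the imputation model leans on their own scores.

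Second sensitivity analysis: shift = fa × (p + 1.0) − fp × p, where fa and fp are the routed shares in the active and placebo arms and the active arm improves by p + 1.0.

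- Equal shares: the p terms cancel and the shift is f × 1.0, that is 0.05 at 5% and 0.10 at 10%.
- Active arm only, f = 5%: 0.05 × 1.5 = 0.075 at p = 0.5, and 0.05 × 3.0 = 0.15 at p = 2.0 (0.24 to 0.47 SE).
- Active arm only, f = 10%: 0.15 to 0.30 (0.47 to 0.95 SE).
- Placebo arm only, f = 5%: −0.05 × 0.5 = −0.025 to −0.05 × 2.0 = −0.10. The present routing would then work against the drug.

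**The case against.** The strongest reply is that the exception is narrow and the effect small. Several stronger readings that a reader might draw are not supported.

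- *All AE withdrawals needing a prohibited drug escape the conservative row.* They do not. The 7.1.7 default is to code AE, and the exception needs the investigator's judgement that the event did not itself justify stopping. The main AE group still gets placebo coding or BOCF.
- *These patients are imputed as if the drug kept working.* This is too strong. The model conditions on screening, baseline and all observed weekly scores, so a patient with poor early scores is not placed at the arm mean. A patient who stops during week 4 may need no imputation, because SAP 6.2.1 sets no minimum number of days for the weekly average.
- *The AEs involved are mostly pain events.* The documents show that three of four prohibited categories are pain treatments, not how often each would be the cause. Protocol 7.3.4.2 refers to other prohibited drugs, such as benzodiazepines. Uncontrolled postherpetic pain may be recorded as lack of efficacy, which Table 2 already covers. Incidental pain unrelated to the ointment could reasonably be treated as missing at random.
- *The shift in one arm's mean can be set against the 1.0-point target.* It cannot, because the target is a between-arm difference and BOCF also applies to placebo. With equal shares much of the shift cancels.
- *The events vanish from the safety output.* 7.1.7 still requires the AE page when an AE is wholly or partly the reason, and the event remains in the general AE tables.

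It can also be said that Table 2's active-arm row refers to any AE and might be read broadly. Nothing in the SAP says that this overrides the coding in 7.1.7, so the ambiguity is itself a reason to clarify. The replies reduce the size and scope but do not remove the mismatch.

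**Conclusion.** The mismatch is real and follows from the text: an AE-driven exit under the 7.1.7 exception gets the same imputation as an unrelated withdrawal in both sensitivity analyses, contrary to the stated aim of the first. It is an inexpensive improvement, not a threat to the trial. The primary analysis and sample size are untouched.

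The effect is probably small. With equal routing in both arms and a gap of up to 1.0 point, the contrast moves by about 0.05 point at 5% routed and 0.10 at 10%, and by less where early scores are observed. Five and 10 percent would already be a quarter and a half of the 22 planned dropouts per arm (5.5/22 and 11/22). One or two patients per arm would move it by 1/110 to 2/110, about 0.01 to 0.02 point. Larger shifts in the second analysis need the cases to fall mainly in the active arm, which nothing in the documents suggests. All of this rests on assumed frequencies, gaps and placebo improvement, and on the termination page being the source of the reason.

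**What to change.** Before unblinding, state in SAP 6.2.3 and Table 2 that prohibited-medication withdrawals linked to an AE or to pain are handled in the AE / lack-of-efficacy row in all arms. Under that row, such patients get placebo-coded imputation (active arms) in the first analysis and BOCF (every arm) in the second. Identify them from the action-taken and treatment fields for the AE (Protocol 7.1.2) and the recorded medication indication (Protocol 5.3). Leave unrelated prohibited-medication withdrawals under other reasons; moving all of them would apply BOCF to exits that have nothing to do with tolerability or pain.

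Name the CRF field that supplies the reason, report the number of reclassified patients by arm, and count the AE-linked cases in Table 15.3.8 or footnote them there.

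The cost is a change to Table 2 and one derivation rule using data already collected. The downside is slightly more conservative sensitivity estimates. Patient management, the 7.1.7 coding rule and the sample size stay as they are.

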9.3.4. Per Protocol Population

The PP population will include all subjects in the FAS who have not had major protocol deviations (ie, protocol violations). Protocol violations will be determined before unblinding. The PP Population will serve as the supportive population for efficacy analyses.

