9.6.1.2. Sensitivity Analysis

Sensitivity analysis on the primary efficacy variable, while taking discontinuation reason and rescue medication usage into consideration, may be performed.

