11.1.2. Protocol Deviations

A protocol deviation is any change, divergence, or departure from the study design or procedures defined in the protocol.

Important protocol deviations, referred to as protocol violations, are a subset of protocol deviations that may significantly impact the completeness, accuracy, and/or reliability of the study data or that may significantly affect a patient's rights, safety, or well-being. Protocol violations include enrolling patients in violation of key eligibility criteria designed to ensure a specific subject population; failing to collect data necessary to interpret primary endpoints; noncompliance to study drug administration; use of prohibited medications; or any other deviations that may have an impact on the processes put in place for the care and safety of the patients or compromise the scientific value of the trial. Protocol violations will be identified and recorded by study site personnel on the CRF. All protocol violations will be reported to the responsible IEC/IRB, as required.

When a protocol violation is reported, the Sponsor will determine whether to discontinue the patient from the study or permit the patient to continue in the study, with documented approval from the medical representative. The decision will be based on ensuring the safety of the patient and preserving the integrity of the study.

Deviations from the inclusion/exclusion criteria of the protocol are **not** prospectively granted by the Sponsor. If study site personnel learn that a patient who did not meet protocol eligibility criteria was entered into a study, they must immediately inform the Sponsor of the protocol violation. If such patient has already completed the study or has withdrawn early, no action will be taken but the violation will be recorded. If such patient is still participating in the study, a determination will be made by the sponsor and the investigator as to whether it is in the best interest of the patient to continue in the study.

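### A withdrawal-coding exception (protocol 7.1.7) can move adverse event patients out of the conservative imputation row, and SAP 3.4 lets prohibited prescription analgesic users stay in the per-protocol set

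*Protocol*

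**What the plan says.** **Reason for withdrawal.** Protocol 7.1.7 has the termination page show an adverse event whenever it is one of several reasons. The one exception is an event the investigator judges not severe enough to stop for, but which needs a prohibited drug. In that case "the reason for discontinuation would be need to take a prohibited medication, not the adverse event".

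**Imputation.** Protocol 9.6.1.2 says a sensitivity analysis "while taking discontinuation reason and rescue medication usage into consideration, may be performed". SAP 6.2.3 plans two, the first under missing at random while "taking into account of potential bias towards the active arm for patients who withdrew from the study due to adverse events". In sensitivity 1 the treatment code "will be coded to 1 (placebo) for those in the active arms withdrawn from study due to an adverse event or lack of efficacy". In sensitivity 2 the same two reasons trigger baseline carried forward (BOCF) in all arms. For the active arms, everyone else who left falls in the Table 2 row "Discontinued due to other reasons" and receives ordinary multiple imputation in both analyses; the placebo arm has an equivalent row. There is no row for prohibited medication.

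**Per-protocol set.** Protocol 9.3.4 admits FAS patients "who have not had major protocol deviations (ie, protocol violations", and 11.1.2 lists among violations "use of prohibited medications; or any other deviations". Section 11.1.2 does not make removal automatic: "the Sponsor will determine whether to discontinue the patient from the study or permit the patient to continue in the study". SAP 3.4 defines the set by four criteria: eligibility, rescue use, at least 4 daily scores in days 22 to 28, and at least 70% compliance between visits 4 and 5. Its preface gives the SAP precedence over the protocol.

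**The concern.** The two sensitivity analyses are built to act on the reason for discontinuation. A case report form convention then decides which adverse event patients they act on. The drugs banned in protocol 5.3 are mainly analgesics, so a patient who leaves under the 7.1.7 exception may well be in pain. For that patient, missing at random is a less comfortable assumption for the week 4 score, yet neither analysis would depart from it.

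The per-protocol gap is separate. A supportive set meant to exclude violators can keep a patient whose week 4 pain score was lowered by a banned analgesic.

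**Working it through.** **Step 1. Follow a 7.1.7 patient through Table 2** (taking the row from the recorded reason):

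| Arm | Analysis | If coded adverse event | As coded under 7.1.7 |
|---|---|---|---|
| Active | Sensitivity 1 | imputed as placebo | imputed with own arm |
| Active | Sensitivity 2 | BOCF | multiple imputation |
| Placebo | Sensitivity 1 | multiple imputation | multiple imputation |
| Placebo | Sensitivity 2 | BOCF | multiple imputation |

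The coding changes both analyses for active patients and only sensitivity 2 for placebo patients.

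**Step 2. Follow a prohibited analgesic user through SAP 3.4.** Through criterion 1 (eligibility), protocol exclusion r covers over-the-counter analgesics, d covers analgesics at entry without washout, and j covers Class Ic drugs. Exclusion r might be read to cover any topical therapy. None covers a prescription oral analgesic started on treatment. Criterion 2 concerns rescue medication only. Criterion 3 removes most patients who stop before about day 25. What remains is the patient who takes the drug and is allowed to continue.

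**Step 3. Reproduce the plan's figures** (protocol 9.2: difference 1.0, SD 2.35, two-sided 5%, 80% power). A two-sample t-test needs 87.66, so 88 per arm; power at 88 is 80.2%. With 20% dropout, 88/0.8 = 110. The stated figures hold. SE = 2.35 × √(2/88) = 0.354.

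**Step 4. Size in sensitivity 1.** The documents give no frequency, so assume a share of 5% of an active arm (5.5 of 110), a constant effect of 1.0 at weeks 1 to 4, and weekly AR(1) correlation r. With k the last observed week, moving these patients to the placebo-coded row shifts the estimate towards no effect by share × (1 − r^(4−k)).

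| r | k = 1 | k = 2 | k = 3 |
|---|---|---|---|
| 0.5 | 0.0438 | 0.0375 | 0.0250 |
| 0.8 | 0.0244 | 0.0180 | 0.0100 |
| 0.9 | 0.0135 | 0.0095 | 0.0050 |

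That is 0.01 to 0.12 SE. A simulation with sequential regression imputation (400,000 per arm, r = 0.8) agreed with the formula: 0.0244, 0.0180 and 0.0099.

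**Step 5. Size in sensitivity 2.** Let pa and pp be the affected shares in active and placebo, and c the placebo improvement, assumed 0.5 to 2.0 points. The active arm improves by c + 1. Moving from multiple imputation to BOCF shifts the estimate towards no effect by pa × (c + 1) − pp × c.

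| pa / pp | c = 0.5 | c = 1 | c = 2 |
|---|---|---|---|
| 5% / 5% | 0.050 | 0.050 | 0.050 |
| 5% / 2% | 0.065 | 0.080 | 0.110 |
| 2% / 5% | 0.005 | −0.010 | −0.040 |

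A negative value favours active. In SE units, 0.05 is 0.14 and 0.11 is 0.31.

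**Step 6. Effect on a conclusion.** At an estimate of 1.0, z = 1.0/0.354 = 2.82 and p = 0.005. After the largest shift, 0.89/0.354 = 2.51 and p = 0.012. Only near the line does a shift matter: an estimate of 0.72 gives p = 0.042, and 0.05 less (0.67) gives p = 0.059.

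**The case against.** - **The group is narrow.** It needs an event not worth stopping for that still requires a drug on a short list. Lack of efficacy already has the conservative row, and protocol 7.1.9 lets some patients continue after an adverse event. An analgesic for unrelated pain is an obvious example, and missing at random is defensible there. This stands and keeps the effect small.
- **The link to Table 2 is an inference.** The SAP does not say that the termination page alone assigns the row. The active-arm row refers to any adverse event, and the form records action taken on study drug for each event, so the event could be recovered. This also stands. But no SAP rule says to recover it, so two programmers could assign the same patient differently.
- **These are supportive analyses in a proof-of-concept trial.** Correct. SAP 5.7 also tabulates violations by category, so prohibited use would be visible. Tabulation does not change who is in the per-protocol set.

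Three stronger readings are tempting, and the documents do not support them:

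- A reader might infer that every removal for a prohibited drug or other violation (protocol 3.9, 11.1.2) bypasses the SAP's safeguard. Where there was no adverse event, no allowance for adverse event withdrawals is bypassed.
- A reader might infer that the per-protocol change is improper because SAP section 10 omits it. The SAP preface says discrepancies will be explained in the clinical study report, and protocol 9.13 allows that report as a place for deviations.
- A reader might infer that collecting the eDiary after an early stop is part of the same fault. It is a separate, consistent on-treatment choice (protocol 4.4) that does not depend on 7.1.7.

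**Conclusion.** The point holds in two limited parts. If Table 2 rows follow the recorded reason, the 7.1.7 exception sends some adverse event withdrawals to ordinary missing-at-random imputation in both sensitivity analyses, against the stated aim of SAP 6.2.3. And SAP 3.4 does not exclude a patient who takes a prohibited prescription oral analgesic on treatment and continues, as protocol 9.3.4 would.

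The size of the first part rests on assumed shares, correlation and placebo response, and is probably small: under these assumptions no more than 0.12 SE in sensitivity 1 and 0.31 SE in sensitivity 2. It would alter a reading only for a result close to the 5% line. No size can be given for the per-protocol part.

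A reader might infer that the present coding always flatters the active arms. The documents do not show this. In sensitivity 2 the direction depends on how many such patients each arm has, and the correction can favour active. Nor is the primary MMRM or any power figure put in doubt.

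**What to change.** 1. In SAP 6.2.3 and Table 2, state that withdrawals under the protocol 7.1.7 exception (an adverse event that led to need for a prohibited drug) belong to the adverse event/lack-of-efficacy row: placebo-coded for active arms in sensitivity 1, BOCF in both active and placebo arms in sensitivity 2. Do not extend this to discretionary removals without an adverse event.
2. In SAP 3.4, add use during treatment of an analgesic prohibited by protocol 5.3 as a per-protocol exclusion, in line with protocol 9.3.4.

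Both should be settled before unblinding. The cost is a minor change to the imputation code and a slightly smaller per-protocol set. Sample size, assessments and the primary analysis do not change.
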